### **7.5.3. Grade 4 Laboratory Abnormality or Clinical Event**

- For a Grade 4 clinical event or clinically significant Grade 4 laboratory abnormality confirmed by repeat testing that is considered related to investigational medicinal product, investigational medicinal product should be permanently discontinued and the subject managed according to local practice. The subject should be followed as clinically indicated until the laboratory abnormality returns to baseline or is otherwise explained, whichever occurs first. A clinically significant Grade 4 laboratory abnormality that is not confirmed by repeat testing should be managed according to the algorithm for the new toxicity grade.
- Investigational medicinal product may be continued without dose interruption for a clinically non-significant Grade 4 laboratory abnormality (e.g., Grade 4 CK after strenuous exercise, or triglyceride elevation that is non-fasting or that can be medically managed) or a clinical event considered unrelated to investigational medicinal product.

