### **7.5.2. Grade 3 Laboratory Abnormality or Clinical Event**

- For Grade 3 clinically significant laboratory abnormality or clinical event, investigational medicinal product may be continued if the event is considered to be unrelated to investigational medicinal product.
- For a Grade 3 clinical event, or clinically significant laboratory abnormality confirmed by repeat testing, that is considered to be related to investigational medicinal product, investigational medicinal product should be withheld until the toxicity returns to  $\leq$  Grade 2.
- If a laboratory abnormality recurs to  $\geq$  Grade 3 following rechallenge with investigational medicinal product and is considered related to investigational medicinal product, then investigational medicinal product should be permanently discontinued and the subject managed according to local practice. Recurrence of laboratory abnormalities considered unrelated to investigational medicinal product may not require permanent discontinuation.

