#### **Elevated Liver Enzymes, Normal or Stable relative to baseline Liver Function Tests**

If ALT levels are elevated (i.e.,  $> 2 \times$  baseline and  $> 10 \times$  ULN) with normal or stable total bilirubin and INR relative to baseline, the subject may remain on study medication and should be monitored weekly as long as ALT levels return to normal or baseline level.

During monitoring, if the ALT values remain persistently elevated, the investigator should discuss with the Gilead Medical Monitor whether the study drug should be discontinued.

For subjects with bridging fibrosis or cirrhosis, study drug discontinuation with treatment-free follow-up is to be avoided due to the potential risk of exacerbation of hepatitis in the setting of low hepatic reserve which could lead to decompensation. Subjects with bridging fibrosis or cirrhosis should be placed on commercially available HBV therapy following study drug discontinuation.

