### **Elevated Liver Enzymes, Elevated Liver Function Tests**

If ALT values are elevated (i.e.,  $> 2 \times$  baseline and  $> 10 \times$  ULN), and total bilirubin is confirmed to be  $2 \times$  baseline value, and INR is 0.5 above baseline, provided both are  $> ULN$ , the investigator should consider discontinuing study medication (upon discussion with the Gilead Medical Monitor, unless the safety of the subject is of immediate concern).

The subject should be monitored weekly as long as ALT, total bilirubin, and INR values remain elevated or above baseline values.

During monitoring, if the ALT values and the liver function tests remain persistently elevated, the investigator should discuss with the Gilead Medical Monitor whether the study drug should be discontinued.

For subjects with bridging fibrosis or cirrhosis, study drug discontinuation with treatment-free follow-up is to be avoided due to the potential risk of exacerbation of hepatitis in the setting of low hepatic reserve which could lead to decompensation. Subjects with bridging fibrosis or cirrhosis should be placed on commercially available HBV therapy following study drug discontinuation.

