Hypouricemia Adult and Pediatric ≥ 1 year	1.5 mg/dL to < LLN 87 μmol/L to < LLN	1.0 to < 1.5 mg/dL 57 to < 87 μmol/L	0.5 to < 1.0 mg/dL 27 to < 57 μmol/L	< 0.5 mg/dL < 27 μmol/L
Infant < 1 Year	N/A	1.0 mg/dl to < LLN- 57 μmol to < LLN	0.5 to < 1.0 mg/dL 27 to < 57 μmol/L	< 0.5 mg/dL < 27 μmol/L
Creatinine**	> 1.50 to 2.00 mg/dL > 133 to 177 μmol/L	> 2.00 to 3.00 mg/dL > 177 to 265 μmol/L	> 3.00 to 6.00 mg/dL > 265 to 530 μmol/L	> 6.00 mg/dL > 530 μmol/L

CHEMISTRY				
	Grade 1	Grade 2	Grade 3	Grade 4
Bicarbonate Adult and Pediatric ≥ 4 Years  Pediatric < 4 Years	16.0 mEq/L to < LLN 16.0 mmol/L to < LLN NA	11.0 to < 16.0 mEq/L 11.0 to < 16.0 mmol/L 11.0 mEq/L to < LLN 11.0 mmol/L to < LLN	8.0 to < 11.0 mEq/L 8.0 to < 11.0 mmol/L 8.0 to < 11.0 mEq/L 8.0 to < 11.0 mmol/L	< 8.0 mEq/L < 8.0 mmol/L < 8.0 mEq/L < 8.0 mmol/L
Triglycerides (Fasting)	NA	500 to 750 mg/dL 5.64–8.47 mmol/L	> 750 to 1200 mg/dL > 8.47–13.55 mmol/L	> 1200 mg/dL > 13.55 mmol/L
LDL (Fasting) Adult	130 to 160 mg/dL 3.35 to 4.15 mmol/L	>160 to 190 mg/dL >4.15 to 4.92 mmol/L	> 190 mg/dL >4.92 mmol/L	NA
LDL (Fasting) Pediatric >2 to <18 years	110 to 130 mg/dL 2.84 to 3.37 mmol/L	>130 to 190 mg/dL >3.37 to 4.92 mmol/L	> 190 mg/dL >4.92 mmol/L	NA
Hypercholesterolemia (Fasting)  Pediatric < 18 Years	200 to 239 mg/dL 5.16 to 6.19 mmol/L 170 to 199 mg/dL 4.39 to 5.15 mmol/L	> 239 to 300 mg/dL > 6.19 to 7.77 mmol/L > 199 to 300 mg/dL > 5.15 to 7.77 mmol/L	> 300 mg/dL > 7.77 mmol/L > 300 mg/dL > 7.77 mmol/L	NA  NA
Creatine Kinase	3.0 to < 6.0 × ULN	6.0 to < 10.0 × ULN	10.0 to < 20.0 × ULN	≥ 20.0 × ULN

\* Calcium should be corrected for albumin if albumin is < 4.0 g/dL

\*\* An overlap between the Grade 1 scale and the Lab's normal range for creatinine may result for Male subjects > 70 yrs. Please follow the Gilead convention of grading any result within the LLN and ULN a 0.

ENZYMES				
	Grade 1	Grade 2	Grade 3	Grade 4
AST (SGOT)	1.25 to 2.50 × ULN	> 2.50 to 5.00 × ULN	> 5.00 to 10.00 × ULN	> 10.00 × ULN
ALT (SGPT)	1.25 to 2.50 × ULN	> 2.50 to 5.00 × ULN	> 5.00 to 10.00 × ULN	> 10.00 × ULN
GGT	1.25 to 2.50 × ULN	> 2.50 to 5.00 × ULN	> 5.00 to 10.00 × ULN	> 10.00 × ULN
Alkaline Phosphatase	1.25 to 2.50 × ULN	> 2.50 to 5.00 × ULN	> 5.00 to 10.00 × ULN	> 10.00 × ULN
Total Amylase	> 1.0 to 1.5 × ULN	> 1.5 to 2.0 × ULN	> 2.0 to 5.0 × ULN	> 5.0 × ULN
Pancreatic Amylase	> 1.0 to 1.5 × ULN	> 1.5 to 2.0 × ULN	> 2.0 to 5.0 × ULN	> 5.0 × ULN

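### For a confirmed, clinically significant, drug-related ALT flare, Protocol 7.5.3 says to stop the drug for good while 7.5.6.1 lets the subject stay on it, and no readable text says which governs

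*Protocol*

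**What the plan says.** Protocol 7.5.3 says of a Grade 4 clinical event, or of a clinically significant Grade 4 laboratory value upheld on repeat, "that is considered related to investigational medicinal product, investigational medicinal product should be permanently discontinued and the subject managed according to local practice". A second bullet relaxes this: "Investigational medicinal product may be continued without dose interruption for a clinically non-significant Grade 4 laboratory abnormality". The examples given there are creatine kinase and triglycerides; ALT is not named.

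Protocol 7.5.6 defines an on-treatment ALT flare as a confirmed ALT above both 2 × baseline and 10 × ULN. Section 7.5.6.1 then recommends treatment changes once the repeat tests are back:

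- Bilirubin and INR normal or stable: "the subject may remain on study medication and should be monitored weekly as long as ALT levels return to normal or baseline level".
- Bilirubin and INR both worsened beyond stated limits: "the investigator should consider discontinuing study medication", after discussion with the Medical Monitor unless safety is an immediate concern.

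Neither branch depends on whether the event is judged drug-related.

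One grade lower, for a related Grade 3 clinical event or confirmed, clinically significant laboratory abnormality, Protocol 7.5.2 says "investigational medicinal product should be withheld until the toxicity returns to" Grade 2 or below.

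The introduction to 7.5 refers all clinically significant toxicities to Appendix 4 and asks that the Medical Monitor be consulted before the drug is stopped, unless immediate action is needed.

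**The concern.** Two parts of the same chapter give different instructions for one patient. Relatedness brings 7.5.3 into play, and in this open-label trial the investigator judges it knowing the arm. Without a stated order of precedence, like cases could be handled differently between subjects or between arms.

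The main stake is safety. Section 7.5.6.1 warns that, in subjects with bridging fibrosis or cirrhosis, stopping followed by a treatment-free period is to be avoided because of possible decompensation. Section 7.5.3 carries no such caution. These are liver transplant recipients.

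The second stake is the primary efficacy endpoint. Under SAP 3.7.2, laboratory values more than 3 days after the last dose of a prematurely stopped drug are no longer on-treatment. Under SAP 6.1.2, missing HBV DNA counts as failure.

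**Working it through.** **1. Do the two rules cover the same patient?** The ALT row of Appendix 5 (Grades 1 to 4 in order) reads "ALT (SGPT) 1.25 to 2.50 × ULN > 2.50 to 5.00 × ULN > 5.00 to 10.00 × ULN > 10.00 × ULN", so Grade 4 starts above 10 × ULN. The flare cut-off is the larger of 10 × ULN and 2 × baseline. Screening allows ALT up to 10 × ULN.

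| Baseline ALT (× ULN) | Grade 4 above | Flare above |
|---|---|---|
| 1 | 10 | 10 |
| 5 | 10 | 10 |
| 7 | 10 | 14 |
| 10 | 10 | 20 |

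Every flare is therefore Grade 4. Up to a baseline of 5 × ULN the cut-offs coincide; above that, some Grade 4 values are not flares and fall under 7.5.3 alone. The overlap is a flare that is also clinically significant and judged related.

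**2. The instructions side by side, for a related and clinically significant ALT**

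| Finding | Generic section | 7.5.6.1 |
|---|---|---|
| Grade 3, confirmed (above 5 to 10 × ULN) | 7.5.2: withhold | does not apply |
| Flare, bilirubin and INR normal or stable | 7.5.3: stop permanently | may continue |
| Flare, bilirubin and INR both worse | 7.5.3: stop permanently | consider stopping |

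Read down the generic column, strictness rises with severity. A site that uses 7.5.2 for Grade 3 and 7.5.6.1 for a flare withholds at the lower value and may continue at the higher one.

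**3. The monitoring sentence.** In the stable branch, weekly monitoring is tied literally to ALT coming back to normal or baseline. In the next branch it is tied to values staying raised. The two durations are opposite as written.

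**4. How often?** The plan states no figure. The inputs are Phase 3 rates from Protocol 1.2.3, with 25 subjects per arm:

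- Expected number = 25 × TAF rate + 25 × TDF rate.
- Confirmed flares, 5/866 and 4/432: 0.144 + 0.231 = 0.38. Chance of at least one = 1 − (861/866)^25 × (428/432)^25 = 0.31.
- Any ALT elevation meeting the flare thresholds, confirmed or not, 16/866 and 9/432: 0.46 + 0.52 = 0.98. Chance of at least one = 0.63.
- Rough proxy for relatedness, Grade 3 ALT-increase adverse events judged drug-related, 3/866 and 1/432: 0.087 + 0.058 = 0.14.

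Phase 3 confirmed a flare at two consecutive visits, whereas Protocol 7.5.6 confirms within 3 days of receiving the result. Any-cause confirmed flares at Phase 3 rates could therefore lie between 0.38 and 0.98.

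**5. Effect on the endpoint.** The Week 24 HBV DNA window is Days 154 to 209 (SAP Table 3-1). With the 3-day allowance, a last dose on or before Day 150 (150 + 3 = 153) leaves no on-treatment value in the window; a later stop matters only if no sample falls in it. One such subject in an arm of 25 who would otherwise have responded costs 1/25 = 4 percentage points under Missing = Failure.

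**The case against.** The strongest reply is structural. Sections 7.5.1 to 7.5.3 are generic grade rules, and the later subsections are topic-specific. Section 7.5.6 has its own definition, confirmation step and treatment modifications, so a reader may take it as the special rule for ALT flares. That is plausible, but no readable text says so, and 7.5.3 does not except ALT.

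Appendix 4, to which 7.5 refers, is only a heading in the available text. It may settle precedence, so absence from the whole protocol cannot be claimed.

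Medical Monitor consultation is a genuine safeguard. It softens the conflict but gives the monitor no written rule to apply.

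The overlap is also narrow. Section 7.5.3 uses *should*, covers only clinically significant and related abnormalities, and allows continuation for non-significant ones. Section 7.2.1 says ineffective treatment is not to be counted as causally related, which takes flares from lost viral control out of 7.5.3. On the other hand, Phase 3 investigators did judge four Grade 3 ALT increases drug-related, so the related category is not empty.

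On the monitoring sentence, the text that follows it, about persistently raised ALT, makes the intent guessable. It is a wording fault, but one in a safety instruction.

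On the endpoint, Missing = Failure keeps the subject in the denominator, SAP 6.1.3 plans a Missing = Excluded sensitivity analysis, and the trial is exploratory with no decision threshold. All of that stands.

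**Conclusion.** The inconsistency holds for a confirmed, clinically significant flare judged related to study drug: one section says stop permanently, while the other says the subject may continue or that stopping should be considered. The readable text does not say which prevails. The reversed monitoring sentence is a separate, smaller fault.

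Three stronger inferences are not supported:

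- **That any related ALT above 10 × ULN must be stopped under one rule and may continue under the other.** The conditions on clinical significance, 2 × baseline, and stable bilirubin and INR all limit the conflict.
- **That one or more cases should be expected.** All Grade 4 ALT values (18/859 and 13/428) give 25 × 18/859 + 25 × 13/428 = 1.28, but that counts unconfirmed values without the 2 × baseline condition. Confirmed flares give about 0.4, with about a 31% chance of at least one.
- **That the choice of section by itself decides responder status.** It does so only if the stop comes before any on-treatment value in the Week 24 window.

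The frequency assumes that Phase 3 rates carry over. Those patients were viremic (median HBV DNA 5.7 and 7.9 log10 IU/mL), whereas this trial enrols subjects below the limit of quantitation, so the number is probably lower, and lower again once relatedness is required. The case for action rests on consistent safety handling, not on a likely shift in the estimate. It is conditional on Appendix 4 not already resolving the point.

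**What to change.** Reconcile Protocol 7.5.2, 7.5.3, 7.5.6.1 and Appendix 4. State in each which section governs ALT values meeting the 7.5.6 criteria, and apply that identically in both arms. Reconcile the weekly-monitoring sentence in the stable branch with its parallel in the next branch. If Appendix 4 already sets precedence, a cross-reference from 7.5.3 and 7.5.6.1 is enough. Which clinical rule applies is for the sponsor and investigators.

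The SAP reports the Week 24 and Week 48 analyses as already done, so the study report should also say which section was applied to any subject with such a flare. SAP 7.2.3 already plans a listing of all ALT elevations, from which these subjects can be found.

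The cost is a few sentences in an amendment and a short statement in the report, with no added procedures or subjects.

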### **7.5.4. Management of Bone Evaluation**

As there is uncertainty surrounding the clinical significance and management of decreases in bone mineral density for chronic HBV-infected patients, Gilead recommends that any subject who has a DXA scan that demonstrates a decrease from baseline of  $> 5\%$  in bone mineral density of the spine region or the hip region be followed per local medical practice at the discretion of the investigator.

### 7.5.5. Management of Potential Nephrotoxicity

eGFRCKD-EPI will be followed post-baseline during the study. All subjects on treatment with baseline eGFRCKD-EPI  $\geq 50$  mL/min/1.73m^2 that decline to  $< 50$  mL/min/1.73m^2 at any post-baseline visit and those with a post-baseline eGFRCKD-EPI  $< 30$  mL/min/1.73m^2 regardless of baseline eGFRCKD-EPI should have serum creatinine measured again within 3 calendar days of receipt of results. At the time of this repeat serum creatinine assessment, Cystatin C will also be measured and the estimated glomerular filtration rate (eGFR) by CKD-EPI (cystatin C) will be calculated and compared with the baseline measurement of this parameter.

#### 7.5.5.1. For subjects on TDF:

- For subjects with baseline eGFRCKD-EPI  $\geq 50$  mL/min/1.73m^2 that decline to  $< 50$  mL/min/1.73m^2 at any post-baseline visit:
  - If the eGFRCKD-EPI is confirmed to be  $\geq 30$  mL/min/1.73m^2 and  $< 50$  mL/min/1.73m^2, the subject will be required to undergo dose modification to every other day dosing of TDF
  - If the eGFRCKD-EPI is confirmed to be  $\geq 30$  mL/min/1.73m^2 and  $< 50$  mL/min/1.73m^2, and the subject has undergone dose modification to every other day dosing of TDF and subsequently develops a confirmed eGFRCKD-EPI  $\geq 50$  mL/min/1.73m^2, the subject may revert to once daily dosing of TDF after discussion with the Gilead Medical Monitor
- For all subjects with a post-baseline eGFRCKD-EPI  $< 30$  mL/min/1.73 m^2 and  $\geq 15$  mL/min/1.73 m^2:
  - If the eGFRCKD-EPI is confirmed to be  $< 30$  mL/min/1.73m^2 and  $\geq 15$  mL/min/1.73 m^2, the subject will be required to undergo dose modification to every 96 hours dosing of TDF
  - If the eGFRCKD-EPI is confirmed to be  $< 30$  mL/min/1.73 m^2 and  $\geq 15$  mL/min/1.73 m^2, and the subject has undergone dose modification to once every 96 hours dosing of TDF and subsequently develops a confirmed CLCr  $\geq 30$  mL/min/1.73 m^2, the subject may revert to every other day dosing of study drug after discussion with the Gilead Medical Monitor
- For all subjects with a post-baseline eGFRCKD-EPI  $< 15$  mL/min/1.73 m^2:
  - If the eGFRCKD-EPI is confirmed to be  $< 15$  mL/min/1.73 m^2, the subject will be required to permanently discontinue treatment according to Section 7.5.5.3

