## GLOSSARY OF ABBREVIATIONS AND DEFINITION OF TERMS

°C	Degrees Celsius
°F	Degrees Fahrenheit
ADV	Adefovir dipivoxil
AE	Adverse event
AhR	Aryl hydrocarbon receptor
AK	Adenylate kinase
ALT	Alanine aminotransferase (SGPT)
ANC	Absolute neutrophil count
ANCOVA	Analysis of covariance
ANOVA	Analysis of variance
AR	Adverse reaction
AST	Aspartate aminotransferase (SGOT)
AUC inf	Area under the concentration versus time curve extrapolated to infinite time, calculated as $AUC_{0-last} + (C_{last}/\lambda_z)$
AUC tau	Area under the plasma concentration versus time curve over the dosing interval (tau)
bsAP	Bone specific alkaline phosphatase
BMD	Bone mineral density
CatA	Cathepsin A
CD4	Cluster of differentiation 4 cells
CD8	Cluster of differentiation 8 cells
Ces1	Caboxylesterase-1
CHB	Chronic hepatitis B
CI	confidence interval
CKD	Chronic kidney disease
CKD-EPI	Chronic kidney disease epidemiology collaboration
CL/F	Apparent oral clearance after administration of the drug
CL Cr	Creatinine clearance
C max	The maximum observed serum/plasma/peripheral blood mononuclear (PBMC) concentration of drug
COBI/C	Cobicistat
CRF/eCRF	Case report form(s)/electronic case report form(s)
CRO	Contract (or clinical) research organization
CTX	C-type collagen sequence
CYP3A4	Cytochrome P450 3A4
DMC	Data Monitoring Committee
DNA	Deoxyribonucleic acid
DXA	Dual energy x-ray absorptiometry
E2	Estradiol
EC	Ethics Committee

E/C/F	Elvitegravir/cobicistat/emtricitabine
eGFR	Estimated glomerular filtration rate
EFV	Efavienz
EKG / ECG	Electrocardiogram
ETV	Entecavir
EU	European Union
EVG	Elvitegravir
FAS	Full analysis set
FDA	(United States) Food and Drug Administration
FEPO 4	Fractional excretion of Phosphate
FRAX ®	Fracture Risk Assessment Tool
FSH	Follicle stimulating hormone
FTC	Emtricitabine
GCP	Good Clinical Practice (Guidelines)
GFR	Glomerular filtration rate
GSI	Gilead Sciences, Inc.
GGT	Gamma glutamyl transferase
Hb	Hemoglobin
HBeAb	Hepatitis B e antibody
HBeAg	Hepatitis B e antigen
HBsAb	Hepatitis B surface antibody
HBsAg	Hepatitis B surface antigen
HBV	Hepatitis B virus
HCC	Hepatocellular carcinoma
HCV	Hepatitis C virus
HDV	Hepatitis D virus
HDPE	High-density polyethylene
hERG	Human ether-à-go-go-Related Gene
HIV	Human Immunodeficiency Virus
IC 50	50% inhibitory concentration
ICF	Informed Consent Form
ICH	International Conference on Harmonisation
IEC	Independent ethics committee
Ig	Immunoglobulin

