#### 7.5.5.2. For subjects on TAF:

- If the eGFRCKD-EPI is confirmed to be  $\geq 15$  mL/min/1.73 m^2, no dose modifications are required

7.5.5.3. For subjects on TAF or TDF:

- All subjects with a confirmed  $eGFR_{CKD-EPI} < 15 \text{ mL/min/1.73 m}^2$  will be required to permanently discontinue treatment
- All subjects with a change from baseline serum creatinine of  $\geq 0.4 \text{ mg/dL}$  must have serum creatinine repeated, with a concurrent urinalysis and urine chemistry, within two weeks of receipt of results

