Table 3-1.	Analysis Visit Windows for HBV DNA, Hematology, Serum Chemistry and Liver Function Tests, eGFR (by CG and CKD-EPI), UACR, UPCR, TmP/GFR, FEPO4, FEUA, Non-fasting Glucose, Weight, and Vital Sign Assessments	17
Table 3-2.	Analysis Visit Windows for Fasting Glucose, Serum Cystatin C and eGFR by CKD-EPI Cystatin C	18
Table 3-3.	Analysis Visit Windows for BMD Results from DXA, Fibrotest, Lipid Panel and HBV Serology	18
Table 3-4.	Analysis Visit Windows for Cr EDTA Renal Scan	18
Table 3-5.	Analysis Visit Windows for Renal and Bone Biomarkers	19
Table 3-6.	Analysis Visit Windows for Post Treatment Assessments.....	19
Table 7-1.	Normal, Osteopenia, and Osteoporosis as Defined by T-score	38
Table 7-2.	Method of Serum Creatinine Correction	41

LIST OF ABBREVIATIONS

AASLD	American Association for the Study of Liver Diseases
AE	adverse event
ALT	alanine aminotransferase (SGPT)
Anti-HBe	antibody to HBeAg
Anti-HBs	antibody to HBsAg
AST	aspartate aminotransferase (SGOT)
BLQ	below the limit of quantitation
BMD	bone mineral density
BMI	body mass index
bsAP	bone specific alkaline phosphatase
CDER	Center for Drug Evaluation and Research
CG	Cockcroft-Gault
CHB	chronic hepatitis B
CI	confidence interval
CKD-EPI	Chronic Kidney Disease Epidemiology Collaboration formula for calculating glomerular filtration rate
CLCr	creatinine clearance
CMH	Cochran-Mantel-Haenszel
Cr EDTA	Chromium ethylenediamine tetraacetic acid
CRF	case report form
CTX	c-type collagen sequence
CV	coefficient of variation
DMC	data monitoring committee
DNA	deoxyribonucleic acid
DXA	dual-energy x-ray absorptiometry
ECG	electrocardiogram
eCRF	electronic case report form
eGFR	estimated glomerular filtration rate
ESDD	early study drug discontinuation
FAS	Full Analysis Set
FDA	Food and Drug Administration
FEPO ₄	fractional excretion of filtered phosphate
FEUA	fractional excretion of uric acid
GFR	glomerular filtration rate
Gilead	Gilead Sciences, Inc.
HBeAb	hepatitis B e antibody
HBeAg	hepatitis B e antigen
HBsAb	hepatitis B surface antibody
HBsAg	hepatitis B surface antigen
HBV	hepatitis B virus
HCV	hepatitis C virus

HDL	high density lipoprotein
HDV	hepatitis D virus
HIV	human immunodeficiency virus
HLGT	high-level group term
HLT	high-level term
IVRS	interactive voice response system
IWRS	interactive web response system
LDL	low density lipoprotein
LLN	lower limit of the normal range
LLOQ	lower limit of quantitation
LLT	lower-level term
LOCF	last observation carried forward
M = E	Missing = Excluded

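### The return from every-96-hours to every-other-day TDF in protocol Section 7.5.5.1 is set on CLCr, an undefined and unscheduled measure, while the matching dose cut is set on eGFR CKD-EPI.

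*Protocol*

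**What the plan says.** Section 7.5.5.1 of the protocol adjusts TDF frequency to renal function in two tiers.

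- **Lower tier, cut.** On a confirmed eGFR CKD-EPI of at least 15 and below 30 mL/min/1.73 m², "the subject will be required to undergo dose modification to every 96 hours dosing of TDF".
- **Lower tier, return.** The next bullet repeats that eGFR condition and continues: "and the subject has undergone dose modification to once every 96 hours dosing of TDF and subsequently develops a confirmed CLCr" of at least 30 mL/min/1.73 m². In that case "the subject may revert to every other day dosing of study drug after discussion with the Gilead Medical Monitor".
- **Upper tier, cut and return.** The cut to every other day applies to a confirmed eGFR CKD-EPI of 30 to below 50. The return needs a later confirmed eGFR CKD-EPI of at least 50, after which "the subject may revert to once daily dosing of TDF after discussion with the Gilead Medical Monitor".

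Section 7.5.5 names eGFR CKD-EPI as the measure followed after baseline. Its confirmation step is that subjects crossing a threshold "should have serum creatinine measured again within 3 calendar days of receipt of results". Section 7.5.5.3 stops treatment on a confirmed eGFR CKD-EPI below 15. That section's other rule, a rise in serum creatinine of 0.4 mg/dL or more, only prompts a retest: such subjects "must have serum creatinine repeated, with a concurrent urinalysis and urine chemistry, within two weeks of receipt of results".

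The protocol glossary expands CLCr as "Creatinine clearance" and the SAP abbreviation list as "creatinine clearance". Neither adds a formula or a collection method.

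**The concern.** A cut and its reversal should sit on one scale, so that a single confirmed result cannot call for one frequency and permit another. In the lower tier they are on differently named scales, and the second has no operational definition. A site or Medical Monitor reading the bullet cannot tell from the documents which number has to reach 30.

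This is a live dosing rule for subjects with severe renal impairment on a drug whose nephrotoxicity motivates the trial. Entry is allowed down to eGFR CKD-EPI 15, and about 40 of the 50 subjects are to be below 60, so the lower tier can be reached. At stake is whether a subject could be put forward for every-other-day TDF while eGFR CKD-EPI still lies in the range that calls for every 96 hours. Every 48 hours is twice the rate of every 96 hours (96/48 = 2).

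**Working it through.** **1. Is CLCr defined or measured anywhere?** The protocol's Appendix 2 lists serum chemistry, eGFR CKD-EPI, cystatin C, and a Cr EDTA scan at Baseline and Week 48. It has no creatinine clearance. SAP Section 7.4.3 gives a Cockcroft-Gault formula, but labels it eGFR CG, states it in mL/min, and does not link it to dosing.

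**2. Which measure does each threshold in Section 7.5.5 use?**

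| Rule | Measure |
|---|---|
| Cut to every other day (30 to < 50) | eGFR CKD-EPI |
| Return to daily (≥ 50) | eGFR CKD-EPI |
| Cut to every 96 hours (15 to < 30) | eGFR CKD-EPI |
| Return to every other day (≥ 30) | CLCr |
| Permanent discontinuation (< 15) | eGFR CKD-EPI |

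If CLCr means eGFR CKD-EPI, the ranges 15 to < 30 and ≥ 30 cannot both hold for one result, and there is no overlap.

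**3. What if it is read as Cockcroft-Gault?** This is an assumption. Formulas from SAP Section 7.4.3, with S = serum creatinine in mg/dL, non-black subjects, and S above κ:

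- eGFR CKD-EPI = 141 × (S/κ)^−1.209 × 0.993^age (× 1.018 if female); κ = 0.9 for men, 0.7 for women
- CG = (140 − age) × weight (× 0.85 if female) / (72 × S)
- Indexed CG = CG × 1.73 / BSA. The conversion, the DuBois body surface area (BSA) and the heights are assumptions, not in the documents.

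Man, 60 years, 80 kg, 175 cm, BSA 1.956 m²:

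- S = 3.10: eGFR = 141 × 0.2242 × 0.6561 = 20.7. CG = 6400/223.2 = 28.7, indexed 25.4. The step-up is not met.
- Later confirmed S = 2.50: eGFR = 141 × 0.2908 × 0.6561 = 26.9, still in the every-96-hours range. CG = 6400/180 = 35.6, indexed 31.4. The step-up is met on either version.

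His CG reaches 30 at S = 6400/(72 × 30) = 2.963, where eGFR is 21.9. His indexed CG reaches 30 at S = 2.963 × 1.73/1.956 = 2.621, where eGFR is 25.4.

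**4. How far does this depend on body size and age?** The table gives the eGFR CKD-EPI at which Cockcroft-Gault reaches 30. Overlap exists only if that value is below 30.

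| Profile (assumed) | BSA, m² | Indexed CG = 30 at S | eGFR there | Overlap, indexed |
|---|---|---|---|---|
| Man 60 y, 80 kg, 175 cm | 1.956 | 2.621 | 25.4 | 25.4–29.9 |
| Woman 60 y, 75 kg, 162 cm | 1.800 | 2.270 | 22.7 | 22.7–29.9 |
| Man 65 y, 65 kg, 170 cm | 1.754 | 2.227 | 29.9 | essentially none |
| Woman 70 y, 50 kg, 155 cm | 1.467 | 1.624 | 31.7 | none |
| Man 70 y, 60 kg, 170 cm | 1.695 | 1.985 | 33.1 | none |

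In the last two rows the Cockcroft-Gault reading would delay the return until eGFR CKD-EPI was already above 30.

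A wider grid (ages 40–70, weights 60–90 kg, both sexes) gives the same picture. At eGFR 25, CG runs from 23.3 to 45.1 mL/min. Indexed values run from 23.9 to 39.0, using assumed heights of 170 cm for men and 160 cm for women and BSA = √(height × weight/3600).

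**The case against.** The strongest reply is that this is an evident slip which context resolves. The printed unit is mL/min/1.73 m², which the SAP attaches to CKD-EPI and not to Cockcroft-Gault. Reading CLCr as Cockcroft-Gault therefore means either ignoring the unit or adding an indexing step that neither document contains. The surrounding bullets and the parallel rule at 50 all use eGFR CKD-EPI. The cut is mandatory and the return optional, so a subject whose later confirmed eGFR is still 15 to < 30 arguably stays under the mandatory bullet. Reversion also needs discussion with the Medical Monitor at a trial planned for about one centre. The SAP reports the Week 24 and Week 48 analyses as already conducted.

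Most of this stands, and it limits the weight of the point. A reader might infer from the printed text that the cut and the return do overlap. The documents do not support that as a fact: it needs the Cockcroft-Gault assumption and a suitable body size, and the printed unit favours the reading with no overlap. The unindexed crossing for the first man (21.9) deserves less weight than the indexed one (25.4) for the same reason.

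What remains is the wording. Both abbreviation lists give CLCr its own meaning, distinct from eGFR, so the term is not a synonym. The Medical Monitor discussion is a safeguard, but no stated criterion tells either party which number to use.

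**Conclusion.** The point holds as a minor inconsistency in an operative dosing rule. One threshold in Section 7.5.5 is printed on an undefined, unscheduled measure, and it probably means eGFR CKD-EPI. Confidence is high on the mismatch in wording. That both conditions can be met by one result is conditional on the Cockcroft-Gault reading, and even then holds only for some subjects.

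Two further inferences are not supported. First, a reader might turn the doubled frequency into a realised dose difference over 24 weeks. It is only a rate: a subject must first fall below 30, be confirmed, be cut, recover, be confirmed again and be discussed. Second, a reader might infer bias in the Week 24 eGFR comparison. Only Arm B subjects (about 25) with a confirmed value of 15 to < 30 can be affected. The documents give no eGFR distribution from which to count them, and nothing shows that any subject was dosed on the wrong measure. No endpoint bias is claimed.

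**What to change.** In Section 7.5.5.1, in the bullet on returning from every 96 hours, replace confirmed CLCr ≥ 30 mL/min/1.73 m² with confirmed eGFR CKD-EPI ≥ 30 mL/min/1.73 m². The cut and the return then exclude each other and match the rule at 50. The change is one term in one bullet. Appendix 2 already schedules eGFR CKD-EPI at every clinic visit, so no visit, test or analysis is added. No other edit is needed.
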